Appendix: Rekonstitution des Fertigarzneimittels tTF-NGR

2. Protocol Synopsis

Title:	PHASE I STUDY OF tTF-NGR IN PATIENTS WITH RECURRENT OR REFRACTORY MALIGNANT TUMORS OR LYMPHOMAS BEYOND ALL STANDARD TREATMENTS							
Short Title:	tTF-NGR Phase I Study							
Sponsor's Study Code:	UKM12_0018							
EudraCT-No.:	2016-003042-85							
Sponsor:	Universitätsklinikum Münster							
Investigator:	PD [name] Department of Medicine A (Hematology, Hemostaseology, Oncology), UKM [name] [name], Germany [contact] [contact] E-mail: [contact]							
Indication:	All solid tumors and lymphomas beyond standard therapy							
Study Design:	Phase I Study							
Investigational Medicinal Product:	tTF-NGR							
Therapy:	Phase I, open label, single arm, non-randomized prospective, monocenter study. tTF-NGR will be given as 1-hour infusion via central venous access once daily for 5 days with a subsequent rest period of 2 weeks and following cycles with dose escalation of 0.5 mg/m² upon judgement of tolerability and therapeutic activity. Starting dose will be 1 mg/m²/day. Patients within the dose-escalation part will be treated in sequence and not in parallel. Individual patients can undergo a maximum of 8 dose-escalations. Dose-escalation is stopped before the maximum number of 8 escalation steps if tumor response, tumor progression or a Dose-Limiting Toxicity (DLT) is observed. In the case of stable disease (SD) and with good tolerability these patients can obtain further cycles without dose-escalation until tumor progression or Dose-Limiting Toxicity (DLT) and the next patient can start with dose-escalation cycles on the highest tolerable dose for the previous patient.							
Objectives:	Primary Objective:							
	To evaluate the maximum tolerated dose (MTD) and the Dose-Limiting Toxicity (DLT) of intravenously (iv) infused daily applications of tTF-NGR for 5 days every 3 weeks in patients with relapsed or refractory cancer, who had obtained all							

	 							
	standard treatment known for their disease entity prior to entron study.							
	Secondary Objectives:							
	1. To determine the perfusion and vascular volume fraction of measurable tumor lesions versus normal reference tissue before and after tTF-NGR application by MRI as a biological surrogate parameter for biological activity of the IMP in the patients treated within the verification cohorts.							
	To obtain pharmacokinetic data of tTF-NGR.							
Endpoints:	Primary Safety Endpoint:							
	Maximum Tolerated Dose (MTD). MTD is the dose below the dose leading to reproducible episodes of Dose Limiting Toxicity (DLT) in at least 2/6 patients. DLT will be characterized by clinical, blood and serum monitoring at specified time points before and during study period.							
	Secondary Efficacy Endpoints:							
	 Occurrence and frequency of inhibition of tumor blood flow as measured by contrast-enhanced Magnetic Resonance Imaging (MRI) in the patients treated in the verification cohorts. Occurrence and frequency of tumor response defined as Complete Response (CR), Partial Response (PR), or Stabile Disease (SD) as defined by RECIST criteria. Descriptive statistics will be used. 							
Planned Number of Study Centers:	1							
Number of Patients/ Sample size:	A minimum of 7 patients depending on occurrence of DLT.							
Inclusion Criteria:	➤ age ≥ 18 years							
	histologically proven or cytologically confirmed solid malignant tumor or malignant lymphoma							
	recurrent or refractory disease after standard therapy and with no known curative or survival-prolonging							

treatment options according to the judgement of the investigators > life expectancy of at least 6 weeks according to the judgement of the investigators Karnofsky performance status >50 > measurable disease with at least one marker-lesion measurable in 2 dimensions by Vascular Volume-Fraction-MRI adequate bone marrow function with absolute neutrophil count > 1000/microliter and platelet count > 50/nl. normal global coagulation parameters (Quick, PTT, TZ, fibrinogen), no prophylactic anticoagulation ➤ adequate liver function (total bilirubin < 3x the upper normal limit (ULN), SGPT/SGOT < 3x ULN) adequate renal function (serum creatinine < 3x ULN)
 > no history of coronary heart disease, stroke, transitory ischemic attacks, pulmonary embolism, or deep vein thrombosis > time elapsed from previous therapy (including other IMPs) > 3 weeks with recovery from side effects > exclusion of central nervous system (CNS) disease and CNS vascular abnormalities by MRI > ability to understand and provide written informed consent written informed consent given > for female patients with child-bearing potential exclusion of pregnancy by adequate testing within 48 hours prior to entry on study females of childbearing potential as well as fertile males must agree to use a highly effective form of contraception (Pearl Index < 1) during the study and for 120 days following the last dose of the IMP **Exclusion Criteria:** clinically significant unrelated illness which in the judgement of the investigators could compromise the patient's ability to tolerate the IMP or be likely to interfere with the study procedures or results

known hypersensitivity reactions to prior application of E. coli-derived material
women with breast-feeding activity
concomitant use of any other investigational agent (agent for which there is currently no approved indication from regulatory authorities)
clinical application of any other drug with known antitumor activity
prophylactic anticoagulation within the last 3 days

Visits:	Days (d), hours (h), weeks (w) post IMP	pre (within 1 w)	at inf.	1 h	5 h	daily	5 d	weekly	repeat cycles (see left)	monthly from end of IMP application	study period end
	History + examination	х	х	х	х	Х	х	х		х	х
	Lab tests (FBC, blochemistry, coagulation)	х	х	х	х	х	х	х		х	х
	Oxygen sats (- = continuous), ECG-monitoring	х	х-	x-	х-	х	х	х		х	х
	Investigator to check eligibility	х						х			
	Informed consent	х									
	Clinical/blood assessment of AE and toxicity	х	х	x	х	Х	х	х		х	х
	Tumor measurements	х								X (without relation to IMP)	х
	MRI, vascular volume fraction* x x x										(x)
	Pharmacokinetics	х	х	X (see below)	х	х	х	х		х	
	НАНА						х				х
	CNS-MRI	х									
Statistical Methods:	Descriptive statistics are performed to characterize MTD (= dose level below DLT occurring in 2/6 patients)										
Financial Support:	Deutsche Krebshilfe, grant 111004										
Schedule	Planned end of Planned end of Planned recruit Duration of sintolerability and	Planned start date of the study (FPFV): 01.11.2016 Planned end date of recruitment (LPFV): 01.11.2017 Planned end date of the study (LPLV): 01.05.2018 Planned recruitment duration: 1 year Duration of single patient participation: according to tolerability and antitumor activity Planned overall duration of the study: 1.5 years									

3. Protocol overview

3.1 Title of Study

PHASE I STUDY OF tTF-NGR IN PATIENTS WITH RECURRENT OR REFRACTORY MALIGNANT TUMORS OR LYMPHOMAS BEYOND ALL STANDARD TREATMENTS

3.2 Protocol summary

Every year worldwide more than 8 million humans die from malignant diseases. The incidence of malignant diseases is increasing. Surgery, radiotherapy and systemic treatment with chemotherapy and immunotherapy have measurable therapeutic effects, but about half of the patients with cancer develop metastasis and have no curative outlook. There is an unmet need for new anticancer treatment strategies using innovative mechanisms of action.

Antiangiogenesis therapy is a relatively new treatment approach for metastatic cancer. It interferes with the development of new vessel formation (neo-angiogenesis), which is essential for the spread of cancer. First agents, such as antibodies targeting vascular endothelial growth factor (VEGF) and small molecule receptor tyrosine kinase inhibitors have been shown to increase overall survival of patients with various tumor histologies for some months. Some agents are approved for medical use in cancer patients. Vascular targeting agents or vascular disrupting agents interfere and destroy already existing tumor vessels. Although interesting results from experimental and early clinical studies exist, no such agent is approved for clinical use.

This document describes a clinical phase I study with an investigational medical product (IMP) inducing thrombosis of blood vessels in solid tumors by a fusion protein consisting of the extracellular domain of tissue factor (truncated tissue factor, tTF) and the peptide GNGRAHA, targeting aminopeptidase N (CD13) and the integrin $\alpha_{\nu}\beta_{3}$ (CD51/CD61) on tumor vascular endothelium. The designed fusion protein tTF-NGR retains its thrombogenic activity and demonstrated in vivo antitumor activity through partial or complete thrombotic occlusion of tumor vessels in human tumor xenograft models. Clinical first-in-man application of low dosages (up to 4 mg/m²) of this targeted coagulation factor revealed good tolerability and decrease of tumor perfusion as measured by magnetic resonance imaging (MRI).

In this phase I clinical trial cancer patients suffering from solid tumors or lymphomas, recurring after and/or refractory against standard treatment are treated intravenously (iv) with increasing doses of tTF-NGR. The objectives of this trial are to evaluate the maximum tolerated dose (MTD) and the dose-limiting toxicity (DLT) of intravenously (iv) infused daily applications of tTF-NGR for 5 days every 3 weeks in patients with cancer, who had obtained all standard treatment known for their disease entity prior to entry on study. Further objectives are to determine the perfusion and vascular volume fraction of measurable tumor lesions versus normal reference tissue before and after tTF-NGR application by MRI as a biological surrogate parameter for biological activity of the IMP and to obtain pharmacokinetic data.

3.3 Trial Objectives

Primary Objectives

To evaluate the maximum tolerated dose (MTD) and the dose-limiting toxicity (DLT) of intravenously (iv) infused daily applications of tTF-NGR for 5 days every 3 weeks in patients with cancer (solid tumors and lymphomas), who had obtained all standard treatment known for their disease entity prior to entry on study.

Secondary Objectives

- 1. To determine the perfusion and vascular volume fraction of measurable tumor lesions versus normal reference tissue before and after tTF-NGR application by MRI as a biological surrogate parameter for biological activity of the IMP. Imaging will be preferentially done in the patients within the verification cohorts in at least one of the treatment cycles as determined by the investigator.
- 2. To obtain pharmacokinetic data of tTF-NGR.

3.4 Investigational Medicinal Product

The IMP is a fusion peptide of N-terminally histidine-tagged human truncated tissue factor (amino acids 1-218) and a C-terminal GNGRAHA binding peptide cloned into the expression vector pET-30(+)a (Novagen), generated by *Escherichia coli* (BL21 DE3) and purified by high performance liquid chromatography (HPLC). Details are summarized in the accompanying Investigational Medicinal Product Dossier (IMPD).

3.5 Trial design

Mono-center, non-randomised, open-label, multiple-dose level phase I trial. The study will be performed in the University Hospital Muenster (UKM). Patients will be treated with tTF-NGR by 1-hour iv infusions via central venous access daily for 5 days every 3 weeks. Starting dose will be 1 mg/m²/day (for justification of this starting dose see IMPD). Dose escalation will be performed within a single patient in 0.5 mg/m²/day steps upon good toleration of the previous cycle. Patients within the dose-escalation part will be treated in sequence and not in parallel. Individual patients can undergo a maximum of 8 dose-escalations. The maximum number of 8 dose escalations is reached only if stable disease (SD) is ongoing upon 8 cycles of therapy. Dose-escalation is stopped before the maximum number of 8 escalation steps if tumor response, tumor progression or a Dose-Limiting Toxicity (DLT) is observed. In the case of SD and with good tolerability these patients can obtain further cycles without dose-escalation until tumor progression or Dose-Limiting Toxicity (DLT) and the next patient can start with dose-escalation cycles on the highest tolerable dose for the previous patient. A patient will undergo no further treatment in case of progressive disease or DLT, unless the DLT is resolved in a responding patient.

Treatment will be followed by MRI tumor perfusion studies before treatment onset, on day 1 (4-6 hours after 1st application), and on day 5. Omission of MRT monitoring during single cycles is allowed as decided by the Investigator with the aim to concentrate MRT monitoring on the higher dose levels, in particular in the patients of the verification cohorts (see below).

Pharmacokinetic monitoring will be performed as outlined below.

3.6 Risk-Benefit Assessment

Every year worldwide more than 8 million humans die from malignant diseases. The incidence of malignant diseases is increasing. Surgery, radiotherapy and systemic treatment with chemotherapy and immunotherapy have measurable therapeutic effects, but about half of the patients with cancer develop metastasis and have no curative outlook. There is an unmet need for new anticancer treatment strategies using innovative mechanisms of action. Patients accrued for this trial are suffering from relapsed or refractory solid tumors or lymphomas after standard therapy with no option

for further standard treatment leading to cure or prolongation of overall survival as judged by the investigator.

The IMP, tTF-NGR, was developed as a new bifunctional protein carrying an essential pro-coagulatory molecule – tissue factor (TF) – via a C-terminal peptide (GNGRAHA) into tumor vessels to induce *selective tumor vascular infarction*. To this end the non-specific membrane anchor of TF was replaced by the CD13-binding NGR motif. CD13 is an aminopeptidase selectively occurring on stimulated and growing endothelial cells (EC), as on tumor endothelial cells, with only limited expression on normal tissue (http://www.proteinatlas.org/ENSG00000166825-ANPEP/tissue). With this molecule we target and accumulate TF in tumor vasculature and induce tumor vascular infarction leading to tumor cell death. tTF-NGR showed robust *in vitro* and *in vivo* activity. tTF-NGR retains complete procoagulatory activity, specifically binds to CD13 on growing EC, it leads to tumor vessel infarction and occlusion with resulting tumor growth inhibition and regression in experimental models. Therapeutic activity of tTF-NGR was independent of tumor histology (e.g. melanoma, lung, breast, sarcoma). Repeated rounds of treatment showed no resistance development. Xenograft experiments in the mouse showed a safe therapeutic window.

The IMP tTF-NGR will be given to few patients with intraindividual dose escalation in sequence until DLT is observed. Subsequently, 5 further patients will be treated sequentially within a verification cohort for DLT. In case a deadly DLT occurs, the verification cohort will be sequentially dosed at the next-lower dose level for safety reasons. Exact dose-escalation is described below. MTD is defined as the dose below observation of 2/6 patients with DLT. MTD dose level will then be verifyed by treating 5 further patients on this dose level below the one on which DLT was observed. This will allow to reduce the risk of DLT to few individual patients and simultaneously avoid treating any patient at dose level so low, that antitumor activity can not occur.

All patients (minimum 7 patients) treated within this protocol can hypothetically reach tumor control by the IMP with a minimum of only 2 patients at risk for DLT. Thus, the potential benefit for the individual patients treated within this study outweighs the risks.

4. Background and Rationale

The scientific background and rationale for performing this phase I trial and the complete set of information on the IMP tTF-NGR are outlined in detail in the Investigational Medicinal Product Dossier (IMPD) on tTF-NGR.

5. Study Design

This is an open-label, single-center phase I study of tTF-NGR in patients with relapsed and/or refractory solid tumors and lymphomas.

Patients will be treated with tTF-NGR by 1-hour iv infusions via central venous access daily for 5 days every 3 weeks. Starting dose will be 1 mg/m²/day. Intraindividual dose escalation will be performed within one single patient in 0.5 mg/m²/day steps upon good toleration of the previous cycle. Patients within the dose-escalation part will be treated in sequence and not in parallel. Individual patients can undergo a maximum of 8 dose-escalations. The maximum number of 8 dose escalations is reached only if stable disease (SD) is ongoing upon 8 cycles of therapy. Dose-escalation is stopped before the maximum number of 8 escalation steps if tumor response, tumor progression or a Dose-Limiting Toxicity (DLT) is observed. In the case of SD and with good tolerability these patients can obtain further cycles without dose-escalation until tumor progression or Dose-Limiting Toxicity (DLT) and the next patient can start with dose-escalation cycles on the highest tolerable dose for the previous patient. A patient will undergo no further treatment if any of the criteria under 7.4 is reached.

Treatment will be followed by MRI tumor perfusion studies at cycles as decided by the Investigator as a surrogate marker for target-hit. MRI tumor perfusion studies will be performed before treatment onset, on day 1 (4-6 hours after application), and on day 5. MRI will be done not in every cycle of every patient, but in every patient of the verification cohorts in at least one cycle.

Toxicity monitoring will be performed according to the most recent version of the CTC criteria.

MTD is the dose below the dose leading to reproducible episodes of Dose Limiting Toxicity (DLT). DLT will be characterized by clinical, blood and serum monitoring at specified time points before and during study period.

Antitumor activity and response will be determined according to RECIST criteria with extent of disease evaluation before and after treatment period and in 3-monthly intervals thereafter, or as defined by clinical needs. Waterfall-analysis for response quantification in % of the marker lesions before treatment onset and at best response will be done centrally by the study radiologist.

Pharmacokinetic monitoring will be done as outlined below.

6. Eligibility criteria and patient registration

6.1 Inclusion Criteria

Inclusion criteria for entry on trial are

- \triangleright age \geq 18 years
- histologically proven or cytologically confirmed solid malignant tumor or malignant lymphoma
- recurrent or refractory disease after standard therapy and with no known curative or survival-prolonging treatment options according to the judgement of the investigators
- > life expectancy of at least 6 weeks according to the judgement of the investigators
- Karnofsky performance status ≥ 50
- measurable disease with at least one marker-lesion measurable in 2 dimensions by Vascular Volume-Fraction-MRI
- adequate bone marrow function with absolute neutrophil count 1000/microliter and platelet count > 50/nl.
- normal global coagulation parameters (Quick, PTT, TZ, fibrinogen), no prophylactic anticoagulation
- ➤ adequate liver function (total bilirubin < 3x the upper normal limit (ULN), SGPT/SGOT < 3x ULN)

- adequate renal function (serum creatinine < 3x ULN)

- > no history of coronary heart disease, stroke, transitory ischemic attacks, pulmonary embolism, or deep vein thrombosis
- \succ time elapsed from previous therapy (including other IMPs) \geq 3 weeks with recovery from side effects

>

- exclusion of central nervous system (CNS) disease and CNS vascular abnormalities by MRI
- ability to understand and provide written informed consent
- written informed consent given
- ➤ for female patients with child-bearing potential exclusion of pregnancy by adequate testing within 48 hours prior to entry on study
- females of childbearing potential as well as fertile males must agree to use a highly effective form of contraception (Pearl Index < 1) during the study and for 120 days following the last dose of the IMP

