7.4 Duration of therapy and Study Period

Treatment with tTF-NGR may continue until one of the following criteria applies:

disease progression

- intercurrent illness that prevents further administration of treatment according to the judgement of the Investigators
- ➤ Occurrence of Dose Limiting Toxicity (DLT), i.e., unacceptable adverse event(s), including Grade ≥ 3 (CTCAE) toxicity for any organ with the exception of the hematopoietic system or Grade 4 for the hematopoietic system attributed to the IMP
- patient decides to withdraw from the study
- general or specific changes in the patient's condition rendering the patient unfit for further treatment in the judgement of the Investigators
- patient is lost to follow-up
- death

Duration of Study Period with follow-up is defined as being

- > from day of signature of Informed Consent to
- day 5 after the start of the last dose level plus 3 months of observation

Patients will be removed from study treatment when any of the criteria listed under section 7.4 applies or the Study Period is completed.

In patients with objective response and good toleration on a specific dose-level reached, or with stable disease upon 8 cycles of therapy, individual dose-escalation will be stopped and patients will be further treated for up to 3 months with the specific dose under which response occurred, or in case of stable disease with the dose at the 8th cycle. If this patient is treated with dose-escalation steps, he/she will be replaced by the next patient to continue the dose-escalation. This is to not add further risk to an individual, when individual benefit is visible. Upon this time Study Period in these individual patients will end. These patients will be eligible for further compassionate-use treatment with the IMP on the dose-level after completion of the Study Period as long as they benefit from treatment in accordance with §34 of the Declaration of Helsinki (2013 Fortaleza, Brazil). Serious adverse events (see paragraph 13 of this protocol) occurring during compassionate use treatment will be reported as within the defined Study Period to guarantee patient safety within this trial.

8. Dosing delays and dose de-escalations in individual patients

De-escalation in individual patients in dosing is not allowed during the Study Period to not interfere with the description of Dose Limiting Toxicity (DLT) and MTD.

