Patients will be evaluated as outlined in the study calendar below. The time-points given are in relation to IMP application. Additional visits will occur as clinically indicated.

Study Calendar for each 5-day cycle

Days (d), hours (h), weeks (w) post IMP	pre (within 1 w)	at inf. stop	1 h	5 h	daily	5 d	weekly	repeat cycles (see left)	monthly from end of IMP application	study period end
History + examination	Х	Х	х	Х	Х	Х	х		х	х
Lab tests (FBC, biochemistry, coagulation)	х	Х	х	х	Х	х	Х		х	Х
Oxygen sats (- = continuous), ECG-monitoring	х	х-	х-	х-	Х	Х	х		х	Х
Investigator to check eligibility	х						х			
Informed consent	Х									
Clinical/blood assessment of AE and toxicity	х	Х	х	х	х	х	х		х	Х
Tumor measurements	х								X (without relation to IMP)	Х
MRI, vascular volume fraction*	Х			Х		Х				(x)
Pharmacokinetics	х	Х	X (see below)	Х	Х	х	х		х	
НАНА						Х				Х
CNS-MRI	х									

^{*,} times are selected by the decision of the investigator, patients in the verification groups are to be evaluated at least in one cycle of therapy

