The immediate reports should be followed promptly by detailed, written reports. In case of death, an autopsy report should be provided, if any. For reported deaths, the investigator should also supply the competent authority and the Ethics Committee with any information, if additionally requested by them.

All Serious Adverse Events will be followed up until resolution or definite outcome. The investigator will be asked to provide interim and follow-up reports, as necessary, if the SAE has not resolved at the time of initial report. The investigator should answer all queries from the Safety Desk as soon as possible.

Monitoring pregnancies for potential Serious Adverse Events

Pregnancy is not serious by itself. However, if a subject has a positive pregnancy test during trial participation, this is reportable on an SAE form in order to identify and follow-up on outcome of pregnancy and on any congenital abnormalities. The report tTF-NGR Phase I Study, Study Protocol, Version 10, 28.07.2016

should be made as soon as the investigator gains knowledge of the event. Follow-up of a pregnancy will be done using specific additional questionnaires supplied by the Safety Desk if required. Information will be collected as far as covered by consent (information about the partner or about a child needs to be covered by consent of the patient's partner, too).

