14.7 Pregnancy, Breast Feeding and Fathering of a Child

There are no data on embryonal or fetal toxicity of tTF-NGR. Since endothelial cells in blood vessels of a growing fetus might express the targets CD13 and □lpha_v□eta₃, treatment of pregnant women has to be avoided. Premenopausal women are only allowed to participate in trials with the IMP under strict birth control and upon a negative result of a pregnancy test. Female patients are considered to have no child bearing potential if they are permanently sterile or post-menopausal. Permanent sterilization methods include hysterectomy, bilateral salpingectomy and bilateral oophorectomy. A postmenopausal state is defined as no menses for 12 months without alternative medical cause.

Female patients of childbearing potential (and male patients with a partner of child bearing potential) must agree to use a highly effective contraceptive method (Pearl index <1) throughout the study period and during the 2 months thereafter.

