Additionally, patients are handed out the patient information sheet incl. the informed consent form which are provided for this study. Patient consent in study participation must be given in writing. Before informed consent is requested, patients are left sufficient time for consideration. They are provided the opportunity for clarification of any study issues.

According to German drug law ("Arzneimittelgesetz") §40(2a) patients are informed that their disease related data are stored in a pseudonymized way and used for scientific evaluations. For study participation they must agree therein in writing.

The informed consent form is dated and signed by the patient and by the investigator. The originally signed informed consent form is archived in the investigator site file. A copy of the signed informed consent form (or a second original) is handed over to the patient together with a copy of the patient information sheet and a copy of the general conditions of the patient insurance.

If the patient is unable to write, in exceptional cases, instead of the written consent required, oral consent in the presence of at least one witness, who was also included when the patient was being informed may be given. The witness may not be anyone working at the study site nor a member of the investigating team. The orally given consent has to be documented in writing, dated and signed by the witness.

In case of any study issue which requires a change of the patient information sheet, patients already included into the study must, if relevant to them, be informed about these issues orally and in writing and their written consent in further study participation must be obtained.

Note: Before undergoing any study specific procedure the patient must have provided written informed consent!

19. Study Administration

This study will be conducted in compliance with the protocol, the International Conference on Harmonisation of Good Clinical Practice (ICH GCP) guidelines and the Declaration of Helsinki (Fortaleza, 2013), the requirements of the current German drug law ("Arzneimittelgesetz"), the current legal provisions regarding data protection, and the principals of Good Clinical Practice.

The present study will not be started before the competent ethics committee has given a favorable opinion and an approval by the competent federal authority has been obtained.

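### The one required pregnancy test is tied to an undefined entry on study, and no repeat is scheduled, so an unrecognised pregnancy could go undetected into later treatment cycles

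*Combined protocol and SAP*

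**What the plan says.** The inclusion criteria (Section 6.1, same wording in the synopsis) require "for female patients with child-bearing potential exclusion of pregnancy by adequate testing within 48 hours prior to entry on study". Section 14.7 allows premenopausal women to take part only under strict birth control and "upon a negative result of a pregnancy test", without saying when the test is done or whether it is repeated. The same section states that there are no embryonal or fetal toxicity data, that growing fetal vessels might express the drug's targets, and that "treatment of pregnant women has to be avoided". Under Section 6.1, women of childbearing potential and fertile men "must agree to use a highly effective form of contraception (Pearl Index < 1) during the study and for 120 days following the last dose".

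The visit table in Section 12 is headed "Study Calendar for each 5-day cycle". It has rows for history, laboratory tests, oxygen saturation and ECG, eligibility, consent, toxicity, tumor measurements, MRI, pharmacokinetics, antibodies and CNS-MRI, but none for a pregnancy test. Section 12.1 names the laboratory tests one by one, without a pregnancy test. It includes standard urinalysis but does not say that this covers one. Section 13.2 sets a reporting rule that applies "if a subject has a positive pregnancy test during trial participation". The treatment-ending criteria in Section 7.4 do not name pregnancy.

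**The concern.** The drug is designed to cause thrombosis in growing vessels, and the protocol itself identifies fetal vasculature as a possible target. It states a clear rule that pregnant women are not to be treated, but schedules a check of that rule only once, before treatment. Treatment then repeats every three weeks, potentially for many months. A team that followed the document to the letter would have no scheduled occasion to detect either a very early pregnancy missed at entry or one conceived between cycles. The reporting rule in Section 13.2 covers positive tests during participation, but no visit is assigned to produce one.

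The anchor of the single test is also loose. Because entry is not linked to the first infusion, the 48-hour limit does not by itself guarantee a recent result on the first day of dosing.

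**Working it through.** The plan states no figure to reproduce. The check sets the sections side by side and adds exposure arithmetic.

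**Inputs**
- Test window: 48 hours before entry (synopsis, Section 6.1).
- Pre-treatment window: within 1 week of the drug. Consent and the eligibility check are both marked there (Section 12 calendar).
- Consent comes before any study-specific procedure: "Before undergoing any study specific procedure the patient must have provided written informed consent" (Section 18).
- Cycle length: 5 treatment days + 16 rest days = 21 days (Section 10).
- Number of cycles: Section 10 gives a maximum of 8 cycles, while Section 5 gives a maximum of 8 escalations, which would mean 9 cycles. Both are carried.
- Further treatment on study: up to 3 months after response or after stable disease at 8 cycles (Section 7.4), taken as 91 days.
- Contraceptive failure: Pearl Index of 1 per 100 woman-years, the upper limit in Sections 6.1 and 14.7, used as an assumed rate.

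**Age of the test at first dose**
- If entry is the first dosing day: 0 to 2 days.
- If entry falls earlier in the pre-treatment week and the test follows consent within that week: up to 7 days.

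**Age of the test at day 1 of cycle 8**
- Cycle 1 day 1 to cycle 8 day 1: 7 x 21 = 147 days.
- Adding 0 to 7 days: 147 to 154 days.

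**Last scheduled infusion**, counting the first dose as day 1; last dosing day of cycle c = 21 x (c - 1) + 5
- Cycle 8: 147 + 5 = day 152. Cycle 9: 168 + 5 = day 173.
- With 91 further days: 152 + 91 = day 243, and 173 + 91 = day 264.

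**Illustrative chance of pregnancy over that time**, 1 - exp(-0.01 x days / 365.25)

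| Days | Probability per woman |
|---|---|
| 26 (2 cycles) | 0.07% |
| 152 | 0.42% |
| 173 | 0.47% |
| 243 | 0.66% |
| 264 | 0.72% |

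If all 7 patients of the minimum sample were women of childbearing potential treated for the longest period, about 7 x 0.0072 = 0.05 pregnancies would be expected. This counts contraceptive failure only, not a pregnancy already present but too early to be detected at entry.

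**Does anything else in the plan schedule a test?** The calendar marks an eligibility check at the pre-treatment visit and weekly. Its content is not stated, and the criterion it would re-check refers to the time before entry, so it does not call for a new test. Contraception lowers the rate of pregnancy but does not detect one. The Section 7.4 criterion on changes making a patient unfit operates only once a pregnancy is known.

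**The case against.** The strongest reply is that the hazard is small and already controlled. Treating a known pregnancy is ruled out by Section 14.7, contraception is mandatory, and an eligibility check recurs weekly. Section 12 permits additional visits as clinically indicated, so an investigator may test at any time. The entry test itself appears in neither the calendar nor the laboratory list, so these lists are not exhaustive for pregnancy testing, and silence there is weaker evidence than it looks. Few patients will reach 8 cycles, since this requires ongoing stable disease in an end-stage population. All of this stands as to size. None of it puts a repeat test on the schedule.

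A reader might infer three stronger things.

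- **That entry means consent.** Section 7.4 starts the Study Period "from day of signature of Informed Consent to". If that were also entry, the test would have to precede consent, in conflict with Section 18, and could be 2 + 7 = 9 days old at first dose and 147 + 9 = 156 days old at cycle 8. The documents do not support this. Study Period is a different term; Section 6.1 lists written consent as a criterion for entry, and Section 6.2 has eligible patients registered afterwards. The natural order is consent, testing, entry. With the test after consent, the limits are about 7 and 154 days.
- **That the plan lets a pregnant patient be dosed.** It does not. Only an unrecognised pregnancy could be dosed.
- **That patients are never retested.** The documents show only that no retest is scheduled.

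**Conclusion.** The point holds as a low-probability but cheaply closed gap in patient safety. One timed test is required, its anchor is undefined relative to dosing, and no repeat is scheduled. The test can be up to about 7 days old at the first infusion and about 147 to 154 days old at day 1 of cycle 8. Treatment on study may run to about day 243 to 264.

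The day counts assume that consent and test fall inside the one-week pre-treatment window, that cycles run every 21 days without delay, and that 3 months is 91 days. The 0.4% to 0.7% per woman rests on the assumed Pearl Index of 1 and should be read as an order of magnitude. The finding does not affect the dose-finding rules or the endpoints.

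**What to change.** Reconcile the synopsis and Sections 6.1, 12, 12.1, 13.2 and 14.7:

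1. In the synopsis and Section 6.1, tie the entry test to the first infusion and state that it follows consent.
2. In the calendar, add a pregnancy-test row for women of childbearing potential, marked in the pre-treatment column for each cycle and at study period end.
3. Add the assay to the Section 12.1 list for the same women.
4. State whether the weekly eligibility check includes pregnancy.

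While these sections are open, the contraception periods should also be reconciled: Section 6.1 gives 120 days after the last dose, Section 14.7 gives 2 months after the study period.

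The cost is an amendment to wording and one assay at visits where laboratory tests are already marked. For a woman completing 8 cycles this is 8 + 1 = 9 tests instead of 1, in what is likely to be a small number of patients.
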